3. Sexually active female participants of childbearing potential must be self-report practicing, at least, one or more the following methods of contraception during the study: intrauterine device (IUD), barrier method in combination with a spermicide, oral/hormonal contraception or abstinence. Female participants of childbearing potential must have a negative urine pregnancy test before receiving study treatment.
4. Written informed consent must be obtained from the participant before study participation.
5. Participant is in good medical health.
6. No current abuse of alcohol or other substance.
7. Capable of giving informed consent.
8. Capable of doing active or sham CES treatments and completing all study requirements independently
9. For compliance, participants need to have completed 85% (36) of treatments to continue participation in the study

Exclusion Criteria:

1. Participant had complications during or after a vaginal or cesarean delivery.
2. Participant had multiple births.
3. Participant meets DSM-V criteria for a mental disorder diagnosis (i.e., schizophrenia, mood disorder, psychosis, anorexia nervosa) as determined by medical history and/or self-report.
4. Participant is clinically judged by the investigator to be at risk for suicide or is acutely suicidal. Participant has attempted suicide one or more times within the past twelve months.
5. Participant has a Hamilton Anxiety Rating Scale (HAM-A14) score above 30 which suggests a very severe clinical level of anxiety symptoms.
6. Participant has a Hamilton Depression Rating Scale (HAM-D17) score above 30 which suggests a very severe clinical level of depressive symptoms.
7. Participant has a psychiatric condition that would require inpatient or partial psychiatric hospitalization.
8. Participant has a significant history of medical disease (i.e. cardiovascular, hepatic (e.g., cirrhosis, hepatitis B or C) renal, gynecological, musculoskeletal, neurological (seizures), gastrointestinal, metabolic, hematological, endocrine, cancer with a metastatic potential or progressive neurological disorders) which could impair reliable participation in the trial or necessitate the use of medication not allowed by this protocol.
9. Participant is pregnant, planning to become pregnant. If a participant becomes pregnant, she will be dropped from the study immediately and followed appropriately.

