10. Participant has had concomitant therapy with another investigational drug, or participation in an investigational drug study within one month before entering this study.
11. Participant has a history of poor compliance or in the Investigator's judgment any participant who is not compliant with the requirements of the study.
12. Participant has had previous trial of CES.

C. Target number of participants (use a minimum target if a specific target is not appropriate for the research design).

A power analysis indicated that 44 (22 participants in treatment group and 22 participants in sham group + 5 (10% for attrition) = 49 participants and would be the minimum needed for this study. Therefore, to account for possible attrition, I will recruit at total of 50 participants (25 subjects in treatment group and 25 subjects in sham group).

D. Non-TAMUCC Participants or Facility

Complete this section **only** if the research will be conducted at a third-party facility **or** participants will be recruited from a third-party site (non-TAMUCC).

Provide the non-TAMUCC location or non-TAMUCC participants to be recruited here (include any permission as an attachment).

Two OB/GYN clinics have agreed to let the Principal Investigator (PI) to recruit participants from their clinics. Letters of support are attached.

R

Recruitment

E(1). Method. Describe methods that will be used to identify the potential participants.

The PI or Research Assistant (RA) will recruit potential participants. Healthy primiparous new mothers in the postpartum period (defined as one year after childbirth) with uncomplicated vaginal or cesarean deliveries who gave birth to healthy infants and have a healthy infant at enrollment in the study. To enroll in the study, participants must score ≥ 2 on both HAM-A14 item 1 (anxious mood) and item 2 (tension) and have a total score of ≥ 16 on the HAM-A14 at baseline. I included participants with lower HAM-A14 scores than is typically used in generalized anxiety disorder (GAD) clinical trials (i.e., HAM-A14 > 20) since the participants included will be a "healthy" population. Using this approach will also improve the generalizability of results to clinical practice.

E(2). Materials. Describe how potential participants will be recruited, what materials will be used (include as an attachment), and how they will be distributed (i.e., who, what, when, where, and how).

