During study Visit 1 the PI or RA will explain the study and answer any questions. Participants will complete a urine pregnancy test. If the urine pregnancy test is negative baseline measures using the HAM-A14, HAM-D17, PSQI19, ISI7, and BIMF20 questionnaires will be completed by the participant with researcher assistance. Participants will then be given an Alpha-Stim® AID CES device kit with a serial number. The PI or RA will instruct participants on how to use the Alpha-Stim® AID CES device; then the participant will be asked to complete a 60-minute treatment. After the completion of the treatment, the participant will be asked about any side-effects or problems the participant may have experienced. Any side-effects information will be recorded on a side-effect form using the subject's words that describe what happened. The protocol for study treatments at home will be explained to you, and any questions will be answered. The participant will be reminded to complete your daily 60 minute CES treatment before the Visit 2 meeting. The participant will receive a \$40.00 Target Gift Card after Visit 1.

• **Visit 2**

At study Visit 2 The participant will be asked to complete a urine pregnancy test. If the urine pregnancy test is negative the participant will be asked to complete the HAM-A14, HAM-D17, PSQI19, ISI7, and BIMF20 questionnaires with researcher assistance. Your log will be reviewed and discussed. The participant will be asked about any side-effects that the participant may have experienced. The protocol for study treatments at home will be reviewed and the following device supplies will be given to you: six new AAA batteries and two 15ml. bottle conducting solution. The process of how to contact the PI or RA will be reviewed. The participant will be reminded to complete your daily 60 minute CES treatment before the Visit 3 meeting. The participant will receive a \$20.00 Target Gift Card after Visit 2.

• **Visit 3/ Last day of treatment**

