At study Visit 3 The participant will be asked to complete a urine pregnancy test. If the urine pregnancy test is negative the participant will be asked to complete the HAM-A14, HAM-D17, PSQI19, ISI7, and BIMF20 questionnaires with PI or RA assistance. The subject's log will be reviewed and discussed as needed. The participant will be asked about any side-effects that the participant may have experienced. The Alpha-Stim® AID CES device and all supplies will be returned to the study team. The participant will receive a \$40.00 Target Gift Card after Visit 3.

C. Equipment. Describe any equipment to be used (e.g., audio, visual), ownership (e.g., TAMUCC, personal), and methods of storage (e.g., password, location).

Study Device: The Alpha-Stim® AID will be used for this study (Figure 1). The Alpha-Stim® AID is a prescriptive device and is FDA cleared for the treatment of anxiety, insomnia, and depression. About the size of a smart phone, the Alpha-Stim AID emits a mild electrical current via ear clip electrodes. The technical specifications for the Alpha-Stim® AID are shown on pages, 15-16. One-half of the devices will be active CES devices (0.5 Hz, 100 μ A (subsensory level), 50% duty cycle, biphasic asymmetrical rectangular waves) using ear clip electrodes. The other one-half of the devices (sham CES) will be identical to the active CES device except the ear clip electrodes will not emit electricity. The FDA has approved the device to be down classified from Class III to Class II (Federal Register, 2014). Subjects will complete a daily one hour CES treatment using ear clip electrodes (Figure 2.) with current set at fixed level of 100 μ A (subsensory level) for active CES treatment group for 6 weeks. The procedure will be the same for the sham group, but the Alpha-Stim® AID ear clips will not emit electricity.

Findings to date indicate that the Alpha-Stim® AID is an effective treatment with broad applications for a variety of syndromes for the management of anxiety, depression, and insomnia, or for the short-term relief of the symptoms of anxiety, depression and/or insomnia. In many cases it is the sole therapeutic method required.

Treatment Regimen:

The treatment regimen is one daily 60 minutes Alpha-Stim® CES treatment using ear clip electrodes for 6 weeks at 0.5 Hz, 50% duty cycle with a fixed current of 100 μ A (subsensory level). The sham CES unit is identical except the sham ear clip electrodes do not emit electricity.

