This study is not expected to involve psychological, social, physical, economic, academic, or legal risks of harm to participants or living children any greater than those ordinarily encountered in daily life. However, if a participant is identified to have severe levels of stress, anxiety, or depression the PI or RA, who is an experienced clinicians, will make referrals to the appropriate resources and health care provider. If side effects occur during the use of CES participants will be referred back to their OB/GYN.

Benefits to Participants; Benefits to Society

A. Benefits to Participants. If applicable, describe the potential benefits to participants as a result of taking part in the research (exclude payments/incentives). If there are no benefits, then state so.

Participants may benefit from this study by becoming more aware of their current mental health status and realizing perceptions about their own health and relationship to maternal functioning.

B. Benefits to Society. Describe the potential benefits to society or contribution to generalizable knowledge as a result of the research.

The information derived from this study can provide important information about the efficacy and adverse effects of a clinical interventions by controlling the variables that could impact the results of the study. It may also provide important information about maternal psychological distress that could translate to health care costs and use.

Waiver of Informed Consent; Informed Consent Process

A(1). Is a waiver of signed informed consent requested? (See Criteria for Waiver of Signed Informed Consent at the end of the HSRP for guidance).
 
If "no," go to B.
	
Y 
	
N 
	
A(2). If "yes," select which criteria applies, then go to B. (See Criteria for Waiver of Signed Informed Consent at the end of the HSRP for guidance).
	
---	-----------------------------------	--	---	--

B. Informed Consent Process. Describe **step-by-step** how informed consent will be obtained from participants (i.e., who, what, where, when, how).

- Note:
- 1) Participants must be given time to review the informed consent and supporting documents and ask questions.
 - 2) For **minor participants**, researchers must obtain both parental informed consent and a separate child assent written at an appropriate reading level.

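### Does an unnamed list of disallowed medication, with no listed record of co-treatment, put the anxiety comparison at risk?

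*Protocol*

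**What the plan says.** **Eligibility.** In the Protocol's Exclusion Criteria, item 8 removes women with a significant history of medical disease on either of two grounds: it could impair reliable participation, or it could "necessitate the use of medication not allowed by this protocol". No section names a drug, class or washout. The only other rule on drug therapy is item 10: "Participant has had concomitant therapy with another investigational drug, or participation in an investigational drug study within one month before entering this study".

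**Visit data.** Under B. Data Collection, after a negative pregnancy test at Visit 2, "the participant will be asked to complete the HAM-A14, HAM-D17, PSQI19, ISI7, and BIMF20 questionnaires with researcher assistance". Then "Your log will be reviewed and discussed", and "The participant will be asked about any side-effects that the participant may have experienced". Visit 3 follows the same pattern with the "HAM-A14, HAM-D17, PSQI19, ISI7, and BIMF20 questionnaires with PI or RA assistance". Neither list has an item for medication, therapy or referral.

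**Referral.** C. Outside Assistance provides that "if a participant is identified to have severe levels of stress, anxiety, or depression the PI or RA" will refer her to suitable resources and a provider. Row 2 of the risk table under B. Mechanism of Protection says much the same for severe anxiety or depression.

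**The concern.** The wording of exclusion 8 presupposes a list that the Protocol does not contain, so staff cannot apply its medication ground from the text alone. The Protocol also opens a route to co-treatment: women enter because they are anxious, HAM-A14 and HAM-D17 are repeated at each visit, and severe distress leads to referral.

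Staff and participants are blinded, so referral cannot follow from knowing the arm, but it can follow from symptoms. If CES works, more sham women would remain severe, be referred and start treatment, which would pull the two arms together on HAM-A14. With about 22 evaluable women per arm, a few such women would count. If nothing is recorded, nobody could say afterwards whether a null result reflects co-treatment, and no later analysis could reconstruct it. That would touch the primary objective, the effect of CES on anxiety.

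**Working it through.** **1. The plan's own figure.** C. Target number of participants gives 44 evaluable women (22 per arm), and 49 after 10% attrition. Check: 44 / (1 − 0.10) = 48.9, rounded up to 49, which agrees. The 44 cannot be reproduced, because the Protocol gives no alpha, sidedness, power, effect size or SD. Assuming a two-sided 5% t-test and 80% power, 22 per arm detects a standardised difference of d = 0.865.

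**2. When a referral can matter.** Visits are three weeks apart over six weeks.

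| Referral arises at | Can it depend on response to CES? | Can it affect the last HAM-A14? |
|---|---|---|
| Visit 1 | No: scores are taken before the first treatment | Yes, but not through response to the assigned device |
| Visit 2 | Yes | Yes, within about three weeks |
| Visit 3 | Yes | No: the final HAM-A14 is already done |

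So, among scheduled visits, only Visit 2 carries the feared mechanism. The woman would have to be referred, be seen, start treatment and respond before Visit 3.

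**3. Who is in the trial.** Exclusions 5 and 6 remove women with HAM-A14 or HAM-D17 above 30. Exclusion 3 removes women with a diagnosed mental disorder by history or self-report, exclusion 4 those at suicide risk, and exclusion 7 those with a condition needing psychiatric hospitalisation. Many women likely to need or already receive treatment are therefore out before randomisation.

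**4. What exclusion 8 still does.** Only its medication ground lacks content. The ground on impaired participation works without a list, and items 3 and 10 work independently of it.

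**5. Scale, under assumptions only.** Let g be the excess share of sham women who start co-treatment and e its effect in SD units. The observed difference becomes d − g × e. With n = 22 per arm and a two-sided 5% t-test:

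| g (assumed) | Excess sham women, 22 × g | e (assumed) | g × e | Diluted d | Power |
|---|---|---|---|---|---|
| 0 | 0 | – | 0 | 0.865 | 80% |
| 0.05 | 1.1 | 0.5 | 0.025 | 0.840 | 77.7% |
| 0.05 | 1.1 | 0.8 | 0.040 | 0.825 | 76.2% |
| 0.20 − 0.05 = 0.15 | 3.3 | 0.5 | 0.075 | 0.790 | 72.5% |
| 0.15 | 3.3 | 0.8 | 0.120 | 0.745 | 67.5% |

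Every input except n is an assumption. The last two rows need a 15-point gap and a full effect of 0.5 to 0.8 SD, which by step 2 would have to arise after Visit 2. Larger gaps would cost more, but nothing in the documents supports a particular gap.

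**6. What recording would change.** The dilution occurs whether or not co-treatment is written down. Recording it would leave the comparison of all women, its estimate and its power exactly as they are. It would help interpretation only.

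**The case for a change.** The strongest case for acting is that eligibility rules and visit data belong in the Protocol, not in an analysis plan, and that no analysis can use treatment nobody recorded. Prevention would cost one form line per visit, and the loss could not be repaired later. The phrase in exclusion 8 also shows that some restriction was intended, so its absence is hardly a deliberate pragmatic choice.

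Part of this stands. The reference is undefined, and no section says that referrals or new treatments are recorded. The rest is weaker:

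- The Protocol is an ethics application written for lay readers, with attachments. The background form, treatment log and side-effect form are not shown. They may already carry a medication field, though nothing says so.
- Exclusion 8 concerns medical disease at entry, while the referral text concerns distress found during the study. They do not contradict each other.
- A false positive from co-treatment would need more of it in the active arm. The symptom-driven route predicts the opposite, so only chance imbalance remains, and randomisation and the significance test already allow for chance.
- A sensitivity analysis of co-treatment is ordinary analysis-plan content, and that plan is not available here.

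**Conclusion.** The two textual observations are correct: exclusion 8 points to medication that the Protocol never names, and the listed procedures at Visits 2 and 3 include no item for concurrent treatment. Neither makes the primary comparison wrong. With blinded 1:1 randomisation and all women compared as assigned, the HAM-A14 contrast remains valid. It then describes CES against sham alongside whatever care women receive, which is a sensible question in this population.

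The possible dilution is confined to treatment that follows a Visit 2 referral and acts within three weeks, in a sample from which the most severe and the diagnosed women have been removed. Its size cannot be derived from the documents. The illustrative fall from 80% power to between 78% and 67% rests on assumed uptake, effect, alpha and baseline power, and should not be read as a loss the trial faces. It would not be regained by naming the medication or adding a form line.

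What remains is missing detail. Staff can ask the sponsor what the phrase in exclusion 8 refers to, and a competent team would normally note referrals and new treatments and describe them by arm. No change to the plan is needed.

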Method for Assigning Subjects to Treatment Groups:

The blocked randomization method will be used to assign participants to active and sham groups (Efid, 2011). Participants will be assigned to CES treatment or sham CES using a 1:1 ratio. Electromedical Products International, Inc. (EPI) will randomize the assignment of appropriate devices to active or sham groups by using a random list of computer generated numbers (1 for active and 2 for sham) in randomly selected block sizes. An EPI device log will be developed as follows: The appropriate device, either active or sham will be assigned to a subject's number in the study (1 – 10, etc.), starting with number 1, in sequential order and the device's serial number will be listed on the EPI device log in the far-right column, Device Serial Number. The EPI log will remain in the EPI office. EPI will enter all device serial numbers on the Investigator device log in the order they are listed on the EPI device log. Study personnel will assign a device to a participant by using the next available device serial number in the order it is listed on the investigator device log. If a participant drops out of the study, that subject's device will be used for the replacement subject. If for some reason, the participant does not return the device, EPI will be notified and they will send the appropriate device, either active or sham, for the replacement subject. The device box will contain an equal number of active and sham CES device kits. The devices will be packed by EPI in the device box in the order of the device serial numbers on the device log. Only EPI has a list of numbers of the devices assigned to the active and sham groups. The PI, RA and participants are blinded to which participants have Alpha-Stim® CES active or sham devices until data analysis is complete. After the last participant completes the study and all data are entered, an individual completely independent of the study and data analysis, for example a database manager, will assign de-identified participants to unidentified groups using the serial numbers provided by EPI. After the completion of data analysis, blinding will be broken.

D. Data Storage. Describe how the data collected will be stored, location(s), how the confidentiality of individually identifiable information will be maintained (if applicable), and who will have access. (For audio and video recordings, include transcripts).

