B. Mechanism of Protection. Describe **every potential risk** to human subjects that may result from participation in the research ("Risk"), and indicate the method or procedure to be used to mitigate the potential risk ("Protection Mechanism"). Consider physical, psychological, social, legal, and economic risks (*e.g., breach of confidentiality, injury, psychological distress, pressure to conform, pressure to participate, etc.*).

	Risk	Protection Mechanism
1.	Breach of confidentiality	Confidentiality will be maintained for the participants by assigning their names as numbers during questionnaire administration and by assigning numbers to the treatment log.
2.	Severe levels of anxiety or depression are identified	The PI or RA, who is an experienced clinicians, will make referrals to the appropriate resources and healthcare provider.
3.	Side-effects: Side-effects seen in approximately 4,541 patients in controlled, open, uncontrolled conditions, and by physician survey and reasonably associated with the use of CES are dizziness (6 cases, 0.13%), skin irritation/electrode burns (5 cases, 0.11%), and headaches (9 cases, 0.20%). Prolonged CES treatment at higher than necessary currents may cause dizziness or nausea that can last from hours to days.	Side-effects are usually mild and self-limiting. Adverse effects are generally seen with treatment at higher than necessary currents. For this study, the active CES unit will be preset by the manufacturer and cannot be independently manipulated. Therefore, higher currents cannot occur. The sham CES unit will be inactive and the ear clip electrodes will not emit electricity. If side effects occur during the use of CES participants will be referred back to their OB/GYN.
4.	As with any therapeutic intervention, not all participants in the treatment group will respond to the Alpha-Stim® AID. Participants randomly assigned to the SHAM group will not receive treatment.	PI or RA will discuss this possibility with participants during informed consent process.
5.		
6.		
7.		
8.		
9.		
10.		

C. Outside Assistance. If applicable, describe any outside assistance available to participants to mitigate the Risks stated above and how this information will be provided (e.g., medical care, counseling, etc).

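### No step collects side effects, or the reason for stopping, from a woman who leaves between visits and is then replaced

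*Protocol*

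**What the plan says.** **When side effects are asked about.** The Data Collection section (item B) sets out the procedures visit by visit.

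- Visit 1, after the supervised first session: "After the completion of the treatment, the participant will be asked about any side-effects or problems the participant may have experienced". The record is a form: "Any side-effects information will be recorded on a side-effect form using the subject's words that describe what happened".
- Visit 2: "Your log will be reviewed and discussed. The participant will be asked about any side-effects that the participant may have experienced".
- Visit 3: "The participant will be asked about any side-effects that the participant may have experienced. The Alpha-Stim® AID CES device and all supplies will be returned".

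The same section puts the visits three weeks apart over six weeks, with an hour's treatment every day. It names no other time at which side effects are sought.

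**What happens when a woman leaves.** Method for Assigning Subjects to Treatment Groups says: "If a participant drops out of the study, that subject's device will be used for the replacement subject". If the device does not come back, the manufacturer sends one of the same type for the replacement. Exclusion item 9 says that a woman who becomes pregnant leaves the study: "she will be dropped from the study immediately and followed appropriately". No exit visit, exit call or record of the reason for stopping is described.

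**What the study is meant to yield.** Benefits to Society says that the study "can provide important information about the efficacy and adverse effects of a clinical interventions".

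**The concern.** The schedule collects side effects only from women who keep attending. A woman who gets headaches or skin irritation at home and gives up has already had her last enquiry, and the event falls after it. Her place then goes to someone else. The chance of being recorded thus depends on the event itself: a side effect bad enough to end participation is less likely to be captured than a mild one.

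The loss need not be equal between arms, because only the active devices emit current. If stopping for a side effect is commoner on active treatment, the comparison is pulled towards no difference.

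The gap lies in collection. A statistical analysis plan can choose which women to count, but it cannot recover an answer that nobody asked for.

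**Working it through.** **1. The Protocol's own figures.** The attrition step reproduces: 44 / (1 − 0.10) = 48.9, rounded up to 49, and 44 × 1.10 = 48.4, also rounded up to 49. The allowance is thus 5 women, and 50 are recruited. The compliance figure also reproduces: 6 × 7 = 42 sessions, 0.85 × 42 = 35.7, rounded up to 36. The Protocol states no expected side-effect rate for this trial and no side-effect denominator, so there is no planned figure to test.

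**2. What is known about a woman, by when she leaves.**

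| Last visit attended | Side-effect enquiries | Home use after the last enquiry |
|---|---|---|
| Visit 1 | 1, straight after the first session | up to about three weeks |
| Visit 2 | 2 | up to about three weeks |
| Visit 3 | 3 | none |

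**3. Other routes by which the information could arrive.**

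- The Visit 2 description mentions how to contact the study staff. That depends on her taking the initiative.
- Mechanism of Protection (row 3) and Outside Assistance refer women with side effects to their OB/GYN. No step brings the information back to the study.
- Device return is a likely contact, but no question is attached to it, and non-return is foreseen.
- Inclusion item 9 ties continuation to 36 treatments, so at most 42 − 36 = 6 may be missed. A woman who cuts back because of a side effect could leave as non-compliant, and no step records why.

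None of these is a required enquiry at the time of leaving.

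**4. Illustration of size.** Two assumptions are not in the Protocol: 5 drop-outs are replaced, and the rate is computed on the 50 completers. Ever treated = 50 + 5 = 55. Let x be the cases recorded among completers and k the drop-outs who stopped for an unrecorded side effect. The completer rate is x/50 and the rate in all treated is (x + k)/55.

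| x | k | x/50 | (x + k)/55 |
|---|---|---|---|
| 0 | 1 | 0% | 1.8% |
| 0 | 3 | 0% | 5.5% |
| 0 | 5 | 0% | 9.1% |
| 1 | 0 | 2.0% | 1.8% |
| 1 | 1 | 2.0% | 3.6% |
| 1 | 3 | 2.0% | 7.3% |
| 1 | 5 | 2.0% | 10.9% |

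The largest gap is 5/55 = 9.1 percentage points (x = 0, k = 5). With x = 1 it is 10.9 − 2.0 = 8.9 points.

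**5. Would the right denominator be enough?** No. With x = 1 and k = 5, counting all 55 women without any exit enquiry gives 1/55 = 1.8%, against a true 6/55 = 10.9%. The numerator has to be collected.

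**The case against.** The best defence is that the Protocol is silent here rather than wrong. Every woman is asked after her first session and again at each visit she attends. She can contact the staff, and the OB/GYN referral presupposes that they hear of problems during use. The consent pages were removed and may hold reporting instructions. Pregnancy withdrawals do have some follow-up. Adverse effects are not among the stated primary or secondary objectives, and the side-effect analysis set may properly sit in the analysis plan, which is not shown.

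Most of this stands, and it rules out several stronger readings that a reader might infer:

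- **That such a woman is never asked.** The text supports only that no step requires it after her last attended visit.
- **That the reported rate excludes the women most affected.** No denominator is stated, and nothing says that a replaced woman's forms are discarded. The replacement rule governs devices.
- **That a few lost events would overturn the safety message.** Suppose 2 active women were lost and replaced, and the 25 completers had no events. The true rate would be 2/27 = 7.4%, but the one-sided 95% upper limit for 0/25 is 1 − 0.05^(1/25) = 11.3%, which already covers it.
- **That a device linked to a complaint is passed on unchecked.** The Protocol relies on the preset output ("the active CES unit will be preset by the manufacturer and cannot be independently manipulated. Therefore, higher currents cannot occur") and reissues drop-outs' devices, but it does not say what happens to one reported as faulty. That is a separate matter from lost data.

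One may also argue that events will be rare. The Protocol cites 6, 5 and 9 cases in about 4,541 patients. If no patient had two effects, that is 20/4,541 = 0.44%, or 25 × 0.0044 = 0.11 expected cases in an arm of 25. But those sources mix controlled, open and uncontrolled conditions with a physician survey. The Protocol does not say how actively side effects were sought in them, so they do not bound the rate here.

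What the defence does not answer is that an event which ends participation between visits has no required route into the data.

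**Conclusion.** The point holds as a gap in data collection. Followed as written, the schedule can miss side effects that arise after a woman's last attended visit and lead her to stop. The loss may differ by arm, and the likely direction is understatement.

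The size is unknown. The figure of about 9 percentage points is the extreme of an illustration. It needs five replaced drop-outs, all stopping for an unrecorded side effect, and a completers-only rate, none of which the Protocol states. With no missed case, the completer rate is not understated at all (2.0% against 1.8%).

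The point bears on the side-effect information only and implies nothing about the anxiety comparison. It should be corrected because the study presents adverse-effect information as one of its benefits, and because the missing data cannot be rebuilt afterwards.

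**What to change.** Add to the Data Collection section:

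- When any woman stops early, for whatever reason, the existing side-effect form and her reason for stopping are completed by phone or at device return. If the device is not returned, phone contact is attempted and the outcome of the attempt is noted.
- Side effects are reported by arm for every woman who had at least one treatment, including those later replaced.

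The means are already in place: the form exists, and Records Retention shows that the investigator and research assistant hold participants' phone numbers.

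The cost is amendment wording and a short extra contact for about 5 women if attrition is as allowed for. Some will not be reached, so the gap narrows rather than closes. The reported side-effect rate may also look less favourable.
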